9.6 Final Data Analyses

Dealing with Score Distribution. We will inspect the distribution of scores to confirm that parametric statistical testing is appropriate. In the event that distributional properties do not support parametric tests, we will compare the results from conventional parametric analyses with (a) results from similar nonparametric testing (e.g., Wilcoxon signed ranks test), (b) results from parametric analyses conducted after the non-normally distributed variables are transformed to improve normality to compare the results with the conventional parametric analyses, and (c) Any illegal values or outliers of $\geq \pm 3z$ will be checked for accuracy with the raw data.

Composite Outcomes. Data reduction in the form of principal component factor analysis (PCA) will be used to derive composite outcomes of CAP, cognition, and everyday function for analyses to reduce the number of comparisons. Baseline data across CAP, cognitive, and everyday function outcomes will be factor analyzed using pairwise deletions. Based on the number of factors derived and factor loadings of the individual measures (.4 or greater), outcome composite scores will be calculated after transforming the baseline data to z scores while taking into account the directional scaling of the items. Post-test scores will be standardized based upon the baseline mean and SD. The baseline factors and loadings will be applied to calculate post-test composite scores.

Preliminary/Descriptive Analyses. Prior to the analyses described below, we will conduct one-way ANOVA or Chi-square analyses as appropriate comparing the randomized groups at baseline on age, race, education, sex, MoCA, GDS, hearing and vision, to ensure that the study randomization procedures were successful. We will also confirm the equivalence of the two randomized conditions by comparing the NICT questionnaire responses. The total across the six items relevant to cognition will be calculated and examined in analyses. If even a marginally significant ($p < .1$) difference is observed for any of these study variables, the pertinent variables will be included as covariates in subsequent analyses.

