In the primary analyses, we examined whether performance changed differentially by random assignment across composite outcomes from baseline to post-test as indicated by a significant group-by-time interaction. Covariates included hearing PTA, visual acuity, and expectations. The group-by-time interactions were not statistically significant for any of the outcomes ($ps > .194$). See Table 2. The results did not change when we included only those who were adherent ($ps > .180$). See Supplementary Table B. Piano training did not significantly enhance CAP, cognition, or everyday function as compared to music listening. We further examined if intervention effects varied by MCI status (Supplementary Table B). There were no significant group-by-time-by-MCI status interactions indicating those with and without MCI did not show differential benefit ($ps > .245$). Thus, MCI did not significantly moderate the effects of piano training.

Effect sizes for piano training as compared to music listening are shown in Table 3. Improvements were not evident in the primary analyses, adherent analyses, or the subsample without MCI on measures of CAP, cognition, or everyday function. Participants with MCI randomized to piano training showed potential small effect sizes for improvement relative to music listening on Trails A, Digit Symbol Coding, and one subtest of the TEA ($ds \geq 0.25$). Raincloud plots of individual assessment and composite variables are included in the supplemental materials.

Results indicated significant effects of time for ATTR in all models and significant effects of time for CAP in the primary and adherent analyses indicating improved performance from pre- to post- training. Significant effects of time were found for cognition and TEA in the primary and adherent analyses, indicating a tendency for decline across time. With respect to covariate effects, CAP, ATTR, and cognitive performance were significantly impacted by hearing. Similarly, Timed IADL and cognitive performance varied significantly by visual acuity. Those with poorer hearing or vision tended to perform worse on these outcomes. Interestingly,

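### The p<.1 baseline screen fires in roughly half or more of soundly randomised trials, so a hit cannot tell failed randomisation from chance, and it picks covariates by imbalance rather than by prognostic value

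*Combined protocol and SAP*

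**What the plan says.** Section 9.6 (Preliminary/Descriptive Analyses) plans one ANOVA or chi-square test per variable, "comparing the randomized groups at baseline on age, race, education, sex, MoCA, GDS, hearing and vision". The stated purpose is "to ensure that the study randomization procedures were successful". The same paragraph adds a comparison of the expectations questionnaire: "We will also confirm the equivalence of the two randomized conditions by comparing the NICT questionnaire responses". One rule then covers all of these. Its trigger is worded "If even a marginally significant ($p < .1$) difference is observed for any of these study variables"; whatever meets it is adjusted for in the later models.

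No multiplicity control is given for these tests and no fixed covariate set is named. Section 6.3.5 says only that the eligibility measures and demographics are possible covariates. Section 9.6 does not say whether a selected covariate enters as a main effect or also with a time interaction.

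Section 14 (Results) shows the rule in use. Hearing was tested separately by ear. The screen fired for left-ear PTA (p=.070), right-ear PTA (p=.010), visual acuity (p=.003) and expectations (p<.001). It did not fire for age (p=.589), education (p=.544) or MoCA (p=.514). The text on the primary models reads: "Covariates included hearing PTA, visual acuity, and expectations".

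**The concern.** The rule is asked to do two jobs, and a significance test between randomised arms suits neither.

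- **Checking the randomisation.** If allocation was sound, every baseline null hypothesis is true, so each test has a 10% chance of p<.1. With eight or nine tests, at least one hit is to be expected.
- **Choosing covariates.** What makes a covariate worth having is that it predicts the outcome. The p-value between arms says nothing about that. A strong predictor of change at p=.11 stays out, and a variable unrelated to change at p=.09 goes in.

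At stake are an Aim 1 and Aim 2 model whose contents are settled only after by-arm data are seen, and precision that the trial could have had from variables it already collects.

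This point covers the eight pre-randomisation variables. The expectations score falls under the same rule but is collected late in training, which is a separate matter.

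**Working it through.** **Inputs from the documents.** Threshold .10 and eight variables (section 9.6); two hearing tests, hence nine tests in practice (section 14); 99 per arm (section 9.3); stratification by MCI status (section 5.5); 268 participants in the baseline comparisons (266 error df + 2). **Assumed, because the documents give no figures:** correlations among the variables, the share of variance in change that they explain, and a 0.4 SD effect. The plan states no false-alarm rate, so it has no figure to reproduce.

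**1. Firing rate, independent tests.**
- Eight tests: 1 - 0.9^8 = 1 - 0.430 = 57.0%; expected hits 8 x 0.1 = 0.8.
- Nine tests: 1 - 0.9^9 = 1 - 0.387 = 61.3%.

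**2. Firing rate allowing for correlation and stratification** (simulated sound randomisations, N=268, one common correlation among the variables):

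| Correlation | Unstratified, one hearing test | Unstratified, each ear | Stratified, one hearing test | Stratified, each ear |
|---|---|---|---|---|
| 0 | 57% | 62% | 52% | 57% |
| 0.2 | 54% | 57% | 50% | 52% |
| 0.3 | 52% | 56% | 47% | 49% |
| 0.5 | 47% | 48% | 39% | 42% |

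With a more varied assumed pattern (left/right PTA .8, age-PTA .4, age-vision .3, education-MoCA .3, age-MoCA -.25), nine variables and no stratification, the rate is 57-59% at N=198. Under stratification MoCA itself is selected in only 1-2% of trials.

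**3. Sensitivity to a real imbalance in one variable.** At d=0.3 that variable's test gives p<.1 in 68% (99 per arm) or 79% (134 per arm) of trials; at d=0.5, in 97% or 99%. At d=0.5 and 99 per arm, at least one of eight independent tests fires in 98.5% of trials, against 57.0% when nothing is wrong. The ratio is 0.985/0.570 = 1.7, so the screen is sensitive to a large imbalance but a hit carries little information.

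**4. Cost when covariates act on change.** The outcome is baseline-adjusted change with unit SD, 99 per arm. Unadjusted, the standardised effect is 0.4 x sqrt(99/2) = 2.81, which gives about 80% power. A fixed set explaining a share R2 divides this by sqrt(1 - R2):
- R2 = 10%: 2.97, about 84% power.
- R2 = 17%: 3.09, about 87%.
- R2 = 27%: 3.29, about 91%.

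The p<.1 rule recovers part of this, because it adjusts when the imbalance is large. Two independent sets of simulations (6,000 and 4,000 trials per setting) compare it with age, education and MoCA fixed in advance:

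| R2 | Power, p<.1 rule | Power, fixed set | Gain in points | Fall in estimator variance |
|---|---|---|---|---|
| 10% | 80.5 / 80.9% | 82.9 / 84.0% | 2.4 / 3.1 | about 5% |
| 17% | 81.2 / 82.3% | 86.7 / 87.3% | 5.5 / 5.0 | 9-10% |
| 27% | 82.0 / 81.4% | 90.3 / 89.4% | 8.3 / 8.0 | about 15% |

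At R2 = 0 there is no gain.

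**5. Cost when covariates enter as main effects only.** Table 14.2 lists hearing, acuity and expectations without time interactions. With two time points, write Y(t) = a + b·group + c·time + d·group·time + e·X + error. The post-minus-pre difference is c + d·group + error: the term e·X cancels. In a complete-data check, the group x time estimate was -0.0763 (SE 0.114) with or without X, and moved to -0.0028 only when X x time was added. In simulations with main effects only and complete data, the p<.1 rule and a fixed set gave identical power. With 24% of post-tests missing at random (section 14 reports 76% completion) and N=268, power was 79.5 v 80.1%, 76.1 v 76.8% and 72.0 v 73.8% (rule v fixed set), a difference of at most 1.8 points.

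**The case against.** The strongest reply is that the rule did little harm here. Its candidates, tests and threshold are written down in advance. Its only stated consequence is an added covariate, and section 14 never concludes that randomisation failed. The power figures in step 4 come from a model of baseline-adjusted change, whereas Table 14.2 uses main effects only. The 10-27% range has no source in the documents. All group x time p-values exceed .194.

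Most of this stands, and it rules out several stronger readings that a reader might infer:

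- *That the screen cannot detect a failure.* It usually flags a gross imbalance (step 3). What it lacks is specificity.
- *That the test as fitted is conservative and underpowered because of this rule.* Step 5 shows that the group x time estimate and SE do not depend on main-effect covariates in complete data, and with missing post-tests the power difference is small.
- *That the reported hits prove faulty allocation.* A smallest p of .003 among nine independent tests has probability 1 - 0.997^9 = 2.7% under sound randomisation. That is unusual, but only the allocation records can settle it.
- *That a better covariate set would overturn the null result.* Nothing in the documents supports this.

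The reply does not rescue the rule. If covariates enter only as main effects, selecting them does almost nothing for the primary test. If they enter so as to act on change, selecting by imbalance gives up precision. In neither case does the screen answer the question about randomisation. Writing the threshold in advance also does not fix which covariates enter.

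**Conclusion.** The point holds as a fault of specificity and of covariate choice. Under sound randomisation the screen fires in roughly 50-60% of trials at low correlation, and in about 39-48% at a common correlation of 0.5. Covariates are then chosen by chance imbalance, which is why age, education and MoCA stayed out of the reported models.

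The price is conditional. It is about 5-15% of estimator variance and about 3-8 points of power at a 0.4 SD effect if three things hold: covariates act on change, age, education and MoCA explain 10-27% of baseline-adjusted change, and there are 99 per arm. It is nil if they explain nothing, and nil for group x time in complete data with main effects only. The change is worth making because it is cheap. It casts no doubt on the direction of the reported findings.

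**What to change.** - Delete the p<.1 rule and the significance tests of baseline variables; describe baseline by arm without tests.
- Verify the randomisation from the process in section 5.5: the list, the seed and code, and the recorded assignments.
- Name in advance a short set chosen on prognostic grounds and measured before randomisation, for example age, education, MoCA, better-ear PTA and near acuity. Enter it in every Aim 1 and Aim 2 model whatever the observed balance, in a form that acts on change: covariate x time terms, or a baseline-adjusted post-test model. State that form in section 9.6.
- For the completed trial, report such a model beside Table 14.2 and label it a post hoc sensitivity analysis. It cannot be called prespecified, because the table already shows which covariates relate to the outcomes.

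The cost is wording plus about five of roughly 190 degrees of freedom, with no new data.

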6 CLINICAL AND LABORATORY EVALUATIONS

Schedule of Evaluations

Evaluation	Measure type	Telephone Screening (≤ 60 days)	Baseline	Clinical Evaluation (≤ 45 days)	Randomization ≤3 wks	Intervention Up to 15 wks	Post-Test >2 days and ≤60 days
Informed Consent	R		X				
Inclusion/Exclusion Questionnaire	I/E	X	X	X			X
Geriatric Depression Scale (GDS)	I/E, C		X				
Demographic Data	C		X				
Montreal Cognitive Assessment (MoCA)	I/E, C		X				
Memory Screening History	IV		X				
Hearing and vision screening Pure-tone Hearing Thresholds Speech Recognition Threshold Near Visual Acuity	I/E, C		X				X
Music Reading Assessment	I/E		X				
Central Auditory Processing Time Compressed Speech 65% Words-in-Noise Test Dichotic Digits Test Dichotic Sentence Identification test ATTR	O		X				X

08/08/2018

Evaluation	Measure type	Telephone Screening (≤ 60 days)	Baseline	Clinical Evaluation (≤ 45 days)	Randomization ≤3 wks	Intervention Up to 15 wks	Post-Test >2 days and ≤60 days
Cognitive Assessment Battery Trail Making Test Digit Coding Verbal Fluency - BHR, Clothes/ Girls' Names, Vegetables/ Musical Instruments (baseline) - FAS, Animals/ Boys' Names, Fruits/Furniture (post-test)	O		X				X
Everyday Functional Assessment Timed IADL Test Test of Everyday Attention	O		X				X
Questionnaires Health Questionnaire Medication Audit Health Changes	SC		X X				X
Adverse Events	R		X	X		X	X
Clinical Evaluation NACC assessments: -Clinical Dementia Rating Scale -Craft Story 21 Recall - Immediate and De- layed -Benson Complex Figure Copy and recall -Multilingual Naming Test -Functional Assessment Scale -Clinician Diagnosis form	SC			X			

08/08/2018

Evaluation	Measure type	Telephone Screening (≤ 60 days)	Baseline	Clinical Evaluation (≤ 45 days)	Randomization ≤3 wks	Intervention Up to 15 wks	Post-Test >2 days and ≤60 days
Lab Assessments (upon IRB approval) CBC Metabolic panel Thyroid Stimulating Hormone (TSH) B12 D Folic Acid MRI (if funding acquired)	IV			X			
Randomization	IV				X		
Advanced Measures of Music Audiation (AMMA)- Day 1 of Training	E					X	
Basic Piano Measure (BPM) OR Music Listening Measure (MLM)- At days 1 and 20 of training	E					X	
General Self-Efficacy and Music Performance Self-Efficacy (At days 1 and 20 of training)	E					X	
Intervention sessions	C					X	
NICT Expectations Questionnaire (Between days 17 and 20 of training)	IV, C					X	
Tester blinding assessment	IV						X

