C=covariate, E=exploratory, I/E=inclusion/exclusion, IV=internal validity, O=outcome, R=regulatory, SC=sample characterization							

6.1 *Timing of Evaluations*

Prior to Randomization: The baseline visit should be scheduled within 60 days of the telephone screening interview. Informed consent must be obtained first at the baseline study visit prior to any data collection. The GDS, MoCA, Music Reading Assessment, as well as hearing and vision screenings must be completed at baseline, prior to the clinical evaluation. The central auditory processing measures, cognitive assessment battery, everyday functional assessments and health questionnaire should be completed at baseline, but missing items can be administered at the beginning of the clinical evaluation, if needed. The clinical evaluation should be completed within 45 days of the baseline visit completion. The NACC assessments will be completed at the clinical evaluation. All the aforementioned measures for the baseline and clinical evaluations should be completed prior to randomization and must be completed prior to the training content being administered. It will be allowable to administer any of the aforementioned measures that are missing from the baseline or clinical visits after randomization, but administration will not be allowed once the participant has received any piano or music listening training.

Prior to Training Content: Any biomarker assessments must be completed prior to training content (blooddraw, mri, etc.). The general and music self efficacy measures can be administered at either baseline or after randomization on day 1 of training, but must be administered prior to participants receiving any piano- or music listening- content training. If the basic piano or music listening measures are administered prior to randomization, the participant will be withdrawn from the trial and a protocol deviation will be noted. The pre-training basic piano and music listening measures must be administered after randomization and must be administered before training content is delivered. If any of the aforementioned baseline, clinical, or pre-training measures are administered after the training content began, a protocol deviation will be noted. Such measures will be coded as missing and will not be used in analyses.

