Intervention Content: The AMMA should be administered on day 1 of training, but it will be allowable to administer the AMMA within the first three training sessions. The NICT questionnaire should be administered between days 17 and 20 of training, but can be administered at the beginning of the post-test visit if it not completed during the intervention phase. The NICT questionnaire must be administered prior to the post-test assessments of CAP, cognition, or everyday function. If the NICT questionnaire is administered after the post-test assessments of CAP, cognition, or everyday function a protocol deviation will be noted. In this instance the NICT questionnaire will be coded as missing and will not be used in analyses. The post-training basic piano measure and music listening measure must be completed after all training content is delivered and prior to the post-test assessment visit. The trainer should confirm with the study coordinator that all scheduled intervention sessions have been completed and the basic piano or music listening assessments are completed prior to the post-test visit. The post-test visit can be rescheduled, if needed, but must occur within 18 weeks of baseline if no intervention was completed, or within 60 days of training completion date (≥ 16 sessions completed). Participant post-tests will be conducted after the intervention phase for those who complete between 1-15 sessions.

⁶ The sentence “Participant post-tests will be conducted after the intervention phase for those who complete between 1-15 sessions” and “(≥ 16 sessions completed)” was added for clarification.

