6.1.2 Intervention Phase

Within three weeks of baseline or clinical evaluation phase completion for each replicate, the Clinical Research Coordinator and/or Research Assistant Trainers will randomize enrolled participants in collaboration with [name] and schedule their first intervention visit. Participants will complete randomized exercises in groups of up to 10 individuals at in-lab sessions that are 90 minutes in duration, occurring two times a week over the subsequent ~3 months. The goal will be for 95% of the training sessions to be conducted in groups of 3-10 persons. Clas-

ses will be arranged such that those with MCI primarily train together within randomized condition. The intervention phase will continue until 20 total sessions are completed or 15 weeks have passed. The trainers will confirm or reschedule the participant to complete an immediate post-intervention assessment. The trainers will make certain that all scheduled intervention sessions are completed prior to the post-test visit and that no training sessions are scheduled after the post-test visit. Fidelity will be assured as described below (See **Quality Assurance** below).

At the first training sessions the trainers will administer the Advanced Measure of Music Audiation (AMMA), General Self-Efficacy Form, and the Music Performance Self-Efficacy form. Those in the music listening control group will complete the music listening measure while those in piano training will complete the basic piano measure. The training protocols detail all of the procedures and content protocols detail the training arms. Please see: P:\CBCS\CSD CAL\Study 15 Music Training NIA\Trainer Docs\Study 15 Music Training procedure protocol.

Between sessions 17 and 20, the trainers will administer the The Cognitive Training Expectations NICT questionnaire to examine participants' attitudes and expectations about the potential effects of the intervention completed. If a participant does not complete this questionnaire during the intervention phase, it may be completed at the beginning of the post-test visit.

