6.1.3 Post-Test

At the post-test visits, cognition-,CAP- and everyday function outcome measures will be re-administered by blinded Research Assistant Testers. Participants will complete the CAP, cognition, and everyday function measures administered at baseline. Alternative forms will be used, as available. The Tester will complete a form indicating whether or not they know the randomized condition of the participant to assess success of blinding and will confirm continued eligibility. A questionnaire will be administered to check for adverse events during the course of the study. Participants will be encouraged to complete post-test regardless of adherence. We will attempt to complete post test for up to 60 days after the training completion date (≥ 16 sessions completed) or 18 weeks post baseline if intervention was not attempted or completed. Participant post-tests will be conducted after the intervention phase for those who complete between 1-15 sessions.⁶

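### The p<.1 covariate rule puts the end-of-training NICT expectations score into the Aim 1 and Aim 2 models, with no rule for participants who lack one

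*Combined protocol and SAP*

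**What the plan says.** Section 9.6 (Preliminary/Descriptive Analyses) lists age, race, education, sex, MoCA, GDS, hearing and vision for comparison between arms, and adds: "We will also confirm the equivalence of the two randomized conditions by comparing the NICT questionnaire responses". When any of these differs at p<.1, "the pertinent variables will be included as covariates in subsequent analyses". Those analyses include the Aim 1 group x time and Aim 2 group x time x MCI models.

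Timing is set elsewhere. Section 6.1.2: "Between sessions 17 and 20, the trainers will administer the The Cognitive Training Expectations NICT questionnaire". Section 6.1 allows a fallback, since NICT "can be administered at the beginning of the post-test visit if it not completed during the intervention phase". If it is given after the post-test assessments, "In this instance the NICT questionnaire will be coded as missing and will not be used in analyses". Section 6.3.6 says the questionnaire concerns the intervention the participant received, and names expectations as a possible covariate.

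Section 6.1 is strict about baseline, clinical and pre-training measures taken once training content has started: "Such measures will be coded as missing and will not be used in analyses".

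The Intent-To-Treat paragraph of 9.6 relies on a linear mixed model under missing at random to keep participants with incomplete follow-up. Sections 9.6 and 9.7 add pattern-mixture models as sensitivity analyses.

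**The concern.** NICT is the one screened variable collected after training begins. It is a post-randomisation measure that the assigned condition can change, yet it is treated like a baseline covariate.

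The practical harm lies in who can be analysed. A likelihood mixed model keeps a person whose post-test outcome is missing, but standard software drops any record whose covariate is missing. A person who left before session 17 and missed post-test has a baseline outcome and no NICT. Once NICT is in the model, that person goes, although the Intent-To-Treat paragraph says such people are retained. The pattern-mixture analyses are introduced for incomplete follow-up, that is, missing outcomes, and do not cover this case. An analysis labelled intent-to-treat could therefore become, in part, an analysis of people who stayed to the end.

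**Working it through.** **1. Did the rule take effect?** Section 14 reports F(1,214)=15.07 for expectations, p<.001. Recomputed, p=0.00014, far below .1. Section 14 then lists expectations among the primary-model covariates.

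**2. How many lack NICT?** For a two-group F test, N = error df + 2.
- Baseline variables, F(1,266): 266 + 2 = 268.
- NICT, F(1,214): 214 + 2 = 216.
- Without NICT: 268 − 216 = 52, and 52/268 = 19.4%.
- Low case: suppose the 268 still includes the 19 people excluded for head injury, anesthesia or hospitalization, and none of them has NICT. Then 52 − 19 = 33, 268 − 19 = 249, and 33/249 = 13.3%.

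**3. Do the other reported counts show who was in the model?** They do not.
- Table 14.2 gives no N.
- Table 14.3 gives 198 overall, and 268 − 198 = 70, but its change scores need both visits.
- The 76% post-test completion fits either denominator: 0.76 × 268 = 204. Alternatively 268 + 19 = 287, 0.76 × 287 = 218, and 218 − 19 = 199.

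**4. What pre-post correlation r is plausible?** Section 9.3 gives none. Its Aim 1 power (95%, N=198, f=0.10) has noncentrality f²·N·2/(1−r). At r=.7 this is 0.01 × 198 × 2/0.3 = 13.2 and power is 0.951, matching the plan. At r=.5 it is 7.92 and power is 0.800. The simulation uses r of .6 and .7.

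**5. What does dropping these records do?** With standardised scores and no true effect, suppose selective dropout raises the baseline mean of those kept in one arm by μ. The complete-pair difference in change is then biased by −(1−r)μ. With 20% dropout and a logit slope of 1 per baseline SD, μ=0.173, so at r=.7 the bias is −0.3 × 0.173 = −0.052 SD. A mixed-model run of that setting (200 runs) gave −0.048 (Monte Carlo SE 0.0075) with about 214 kept, against 0.004 with all 268 kept.

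Simulations matched to the reported counts (8,000 runs per cell, maximum likelihood) give the absolute bias in SD. Dropout depends on baseline in one arm only, with a logit slope of 0.5 or 1:

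| Case | r=.6, slope 0.5 | r=.6, slope 1 | r=.7, slope 0.5 | r=.7, slope 1 |
|---|---|---|---|---|
| A: 268 people, 198 pairs, 52 of 70 non-attenders lack NICT | 0.033 | 0.060 | 0.026 | 0.045 |
| B: 249 people, 198 pairs, 33 of 51 lack NICT | 0.025 | 0.039 | 0.018 | 0.030 |
| C: 268 people, 218 pairs, 50 non-attenders and 2 attenders lack NICT | 0.037 | 0.063 | 0.026 | 0.048 |

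The sign depends on which arm has the selective dropout. Type I error across these cells is 5.3 to 8.2%. In case A at r=.6 the SE rises from 0.125 to 0.127. Keeping everyone and omitting NICT gives bias within 0.004 of zero. So does an equal slope of 0.5 in both arms.

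**6. Is the covariate adjustment itself harmful?** Among complete pairs, a time-constant main effect does not move group x time. The harm is the lost records.

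**The case against.** **Adjusting for expectations was deliberate.** The Schedule of Evaluations codes NICT as an internal-validity measure and a covariate, and section 6.3.6 agrees. If the harm is only lost records, one sentence on missing covariates would cure it without moving NICT out of the primary model. This has force, and either route would keep the records. It does not make NICT a pre-treatment variable, and a pre-specified covariate still needs a missing-data rule.

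**No dropped record is documented.** The plan names no software for these models, and its stated aim is to use all available data. The participant-flow figure and supplementary tables, which might give model Ns, are not in the text available. This stands as a limit: exclusion is inferred.

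**The 52 may not all be early leavers.** Some may have had late forms coded missing, or be among the 19 exclusions. Non-adherent participants could also supply a score, since "Participants will be encouraged to complete post-test regardless of adherence". With 216 scored against 198 pairs, the counts allow that nobody with paired data was lost. All of this is correct.

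**The bias may be smaller for cognition.** If the composites have SD 10 (an assumption suggested by intercepts near 50) and N=198, then SE = (2/√198) × 10 × √(2(1−r)). The SE of 0.84 for cognition implies r of about .83, where the bias is 0.016 to 0.026 SD. ATTR, the Test of Everyday Attention and Timed IADL imply r of .38 to .56, where it could be larger. Even a bias of 0.063 SD added to cognition gives (0.39+0.63)/0.84 = 1.21, p about .23. Adding 0.098 SD to Timed IADL gives (1.53+0.98)/1.58 = 1.59, p about .11. Neither reaches significance.

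**Conclusion.** The concern holds. The stated rule admits a post-randomisation score that some randomised participants cannot have, and the plan has no provision for its absence. Followed with ordinary mixed-model software, it removes baseline records that the intent-to-treat paragraph says are kept. The reported results show that the rule took effect, with 52 of 268 (19%) lacking the score, or 33 of 249 (13%) on the low reading.

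The consequence for the estimates is modest and conditional. Bias of 0.02 to 0.06 SD, in either direction, requires that records without NICT were dropped and that dropout depended on baseline differently by arm. Neither is documented. With equal dropout mechanisms the bias is about zero, and the cost is a 1 to 2% larger SE. All reported group x time p-values exceed .194, and no conclusion is shown to change. It should be fixed because the intent-to-treat claim cannot be verified without model Ns. Confidence is medium.

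**What to change.** - Remove NICT from the p<.1 covariate rule in section 9.6.
- Run Aims 1 and 2 with covariates measured before training content only, on all eligible randomised participants with any outcome data.
- State how a missing covariate is handled, and report the N of every model.
- Report NICT by arm, and keep the NICT-adjusted model as a labelled sensitivity analysis with its own N.
- Because results are known, label any re-run post hoc.

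The cost is a change of SAP wording and one re-run of existing models. The downside is that the primary model would no longer adjust for unequal expectations, a deliberate feature of the design. That adjustment would appear only in the sensitivity analysis.
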